#### Avoidance of bias:

Qualitative analyses: Qualitative research by its nature is context-rich but not generalizable. Our qualitative sampling strategies including both VAI and Urban groups were designed to include a broad range of PWD and PWOD with diverse experiences. We will use the inter-rater reliability function within NVivo to ensure consistency in coding establishing trustworthiness of the data. Virtual worlds are acknowledged as having a yet to be tapped potential for social, human-centered ethnographic research and represent the emerging field of "cyber anthropology". Second Life is a 'virtual world' that mimics complex physical spaces where people represented as avatars can interact with each other, learn, and express their self identities. Self is defined in reaction to mental perceptions and how we want to be perceived by people in the dominant or alternative social and political culture(s) to which we choose to relate with disabilities existing in the contexts of the normal or an ideal construct. Second Life is a particularly useful vehicle for connection among PWD with limited options to socialize in the natural world where group identification and work for social change is protective and can be empowering to oneself and to ones' larger group. Virtual worlds have been applied successfully in a variety of anthropological studies. Still, some might ask are virtual worlds real? We argue that virtual worlds are not just representations, but are places with "worldness" cohabited and alterable by people interacting and engaging while embodied as avatars. All human culture is virtual as it is superimposed on the natural world. Second Life is a relatively complete "world," and by its graphic interface more analogous to the experienced world outside media, than are telephones, books, and computer games.

Quantitative: ADL and IADL are fundamental. Yet, other activities such as driving and additional unobservable cofounders could bias interpretations. We minimized unobservable confounders by selecting a content-rich data source. Recall bias which in surveys can be problematic is minimized in the MCBS by having people keep records. Around 18% of Medicare beneficiaries refuse to participate in the MCBS which could potentially reduce generalizability. Studies of the MCBS data indicate that bias caused by differences between non-responders and responders was small and substantially reduced by the non-response procedures employed. MCBS cumulative response rates by the fourth year range between 63-68%. Recognizing that lost to follow-up may be more common among those with substantial disabilities, we will include post-stratification weights to minimize potential effects of differential non-response, and adjust the weight further by considering propensity to drop out.

PRINCIPAL INVESTIGATOR (LAST, FIRST, MIDDLE): [name]

We will also impute missing data using SAS callable IVEware software 0.2 through multiple imputation. After generating 5 multiple imputation datasets, we will conduct all analyses allowing inclusion of all subjects. We will compare findings across the different analytical approaches. Also, we acknowledge that this observational design is not causal; however, the mixed methods design and use of large broadly representative populations enhance validity. Finally, it is essential to recognize the essential patient centeredness of this project. We will be addressing patients' perceptions of and beliefs about healthcare quality and physician competence. Conclusions that might be drawn from patient perceptions and professional measures may differ.

**Study population:** See description in study sample section.

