#### Data Analysis

Complex survey design: The MCBS uses a multi-stage clustering sample with unequal sampling probabilities. We will take into account the complex design by using appropriate survey commands in Stata to calculate the correct point estimates and their variances. Specifically, the set of longitudinal weights (RIC X2) allowing analysis of data trends over a two year period and a second set of longitudinal weights (RIC X3) will be applied to two- and three-year outcomes.

Proxies: Proxy responses will be included in all models. About 9.8% of MCBS baseline interviews were conducted by proxies and our previous work indicates that exclusion of proxy responses results in underestimates of disability prevalence. Recognizing this may explain proxy differences we will explore replacing proxy status with reason for proxy use.

Missing data and attrition: See Avoidance of Bias below.

General approach to analysis: Each Aim will describe the sample of Medicare beneficiaries with weighted uni-variable summary statistics appropriate to the distributional characteristics of the variables of interest and bi-variable associations with outcomes. Because of concerns that some variables may be intermediate on causal pathways, to understand associations, we will build etiological models hierarchically. All will control for baseline age, gender, race, ADL or

PRINCIPAL INVESTIGATOR (LAST, FIRST, MIDDLE): [name]

IADL stage, and proxy status. Health conditions and living circumstances will be added sequentially, selected according to associations with functional change, institutionalization, or mortality or according to emergent themes from stakeholder groups. The Goodness-of-Fit (GOF), Deviance and Pearson GOF Statistic, ROC curve, and r-square values as appropriate to each regression will be reported to document model fit of the multinomial regressions. Stata 11.0 (Stata Corp, College Station, Texas) will be used for all analyses (except for multiple imputation as noted below). A 2-sided  $p<.05$  will be used for all final tests of significance.

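### Five imputations leave borderline p-values, and so membership of the Surveillance Tool, partly dependent on the imputation run; about 40 would largely cure this at little cost.

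*Combined protocol and SAP*

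**What the plan says.** The quantitative part of Avoidance of bias describes three layers of handling for non-response and missing data.

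- **Survey non-response and drop-out.** The plan notes that "Around 18% of Medicare beneficiaries refuse to participate in the MCBS" and that "MCBS cumulative response rates by the fourth year range between 63-68" percent. It answers with weights: "we will include post-stratification weights to minimize potential effects of differential non-response", and it will "adjust the weight further by considering propensity to drop out".
- **Imputation.** In addition, missing data are imputed with IVEware. The text continues "After generating 5 multiple imputation datasets", "we will conduct all analyses allowing inclusion of all subjects".
- **Comparison.** "We will compare findings across the different analytical approaches".

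The plan does not list the variables to be imputed. It gives no item-missingness rate, no FMI, no reason for choosing 5, no seed and no check of Monte Carlo error.

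Two other passages use the resulting p-values. Data Analysis sets a two-sided .05 level that "will be used for all final tests of significance". The description of the Patient-Informed Surveillance Tool, under Aim 4, removes candidates at p > .05 by backward selection. It then divides each significant coefficient by the smallest significant one, rounds, and gives non-significant coefficients a score of 0. It does not say how the selection is carried out across several imputed datasets.

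**The concern.** With 5 imputations the between-imputation variance is estimated on 4 degrees of freedom, and the pooled estimate itself carries simulation noise. Both change when the imputation is rerun on the same data.

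For a coefficient far from the threshold this is harmless. The Tool, however, uses a hard cut-off, and its scoring rule passes the effect on. If the smallest retained coefficient is borderline, whether it stays in can change the divisor for every other item, so the whole point score can shift.

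The Tool is the project's final deliverable, and the Replication and Reproducibility section invites other groups to reproduce the findings. A team with the same data and code but a different seed could select different variables.

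**Working it through.** The plan states no efficiency or interval-width figure for 5 imputations, so there is nothing of its own to reproduce.

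**Inputs**
- Number of imputations m = 5, and the two-sided .05 level: from the plan.
- FMI, written g: not in the plan, so assumed. The range used is 0.05 to 0.23.
- The upper end of that range treats in-sample loss as if it were FMI. If the 63% cumulative response includes the roughly 18% who refuse at the outset, loss among those who entered is 1 − 0.63/0.82 = 23.2%. With 68% it is 1 − 0.68/0.82 = 17.1%.
- The lower values, 0.05 and 0.10, stand for imputation of scattered item non-response only.
- A ceiling of 0.37 = 1 − 0.63 is shown for completeness.

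**Interval width relative to unlimited imputations** (Rubin's rules, large complete-data degrees of freedom)

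Width ratio = √(1 + g/m) × t(.975, df)/1.96, with df = (m − 1)/g².

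| g | √(1 + g/5) | df at m = 5 | t/1.96 | Widening, m = 5 | Widening, m = 40 |
|---|---|---|---|---|---|
| 0.05 | 1.005 | 1600 | 1.001 | 0.6% | 0.1% |
| 0.10 | 1.010 | 400 | 1.003 | 1.3% | 0.2% |
| 0.171 | 1.017 | 137 | 1.009 | 2.6% | 0.3% |
| 0.232 | 1.023 | 74 | 1.017 | 4.0% | 0.5% |
| 0.37 (ceiling) | 1.036 | 29 | 1.043 | 8.1% | 0.9% |

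The alternative form of df, based on the proportion of total variance due to imputation, raises the m = 5 figures slightly: 4.5% at g = 0.232 and 9.3% at g = 0.37.

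**Dependence on the imputation run**

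The data were held fixed and only the imputations redrawn. With the unlimited-imputation standard error set to 1:
- the pooled estimate is normal around its unlimited-imputation value z, with variance g/m;
- the between-imputation variance is g × χ²(m − 1)/(m − 1);
- the within-imputation variance is 1 − g;
- the p-value comes from Rubin's pooled t test.

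The simulation SD of the estimate is √(g/m). At m = 5 that is 0.10 standard errors at g = 0.05, 0.14 at 0.10 and 0.22 at 0.232.

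Share of runs in which a coefficient with unlimited-imputation p = .025 fails to reach p < .05:

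| g | m = 5 | m = 40 |
|---|---|---|
| 0.05 | 1% | under 0.1% |
| 0.10 | 7% | under 0.1% |
| 0.171 | 18% | under 0.1% |
| 0.232 | 25% | 0.2% |
| 0.37 (ceiling) | 37% | 2% |

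For a coefficient sitting exactly at p = .05, the central 95% range of p over runs at g = 0.232 is .014 to .17 with m = 5 and .033 to .076 with m = 40.

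**The case against.** The strongest objection concerns the size of the problem. A reader might infer from the fourth-year response rate that missing information reaches 37% and that intervals are therefore 8% too wide. The documents do not support that reading, for four reasons.

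- The 37% is the complement of a cumulative survey response rate. That rate may include initial refusers, who never enter the sample and cannot be imputed. The plan does not define the term.
- Drop-out is also addressed by weighting, and the plan never says that outcomes lost to drop-out are imputed.
- A non-response proportion is not an FMI. FMI varies by coefficient and is usually lower when other variables predict the missing values.
- The fourth-year figure should overstate loss for 1- and 2-year outcomes.

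The preliminary counts do not supply a floor of 14% either (1 − 10,399/12,058). The 10,399 are complete records from panels active in fall 2005, the 12,058 are fall 2006 respondents, and a complete-case share is again not an FMI.

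Nor should the wider intervals be read as wrong. The t reference is the proper allowance for few imputations. The loss is modest efficiency, not bias or poor coverage.

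The other objections carry less weight. Stakeholder input also shapes the Tool, but the .05 removal rule still operates before it. The planned comparison of analytical approaches does not vary the imputation draws, so it will not reveal the instability. Sharing code with a recorded seed would make the result repeatable at any m, but selection would still rest on one arbitrary draw.

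What stands from this side is that the size is uncertain and probably small for most coefficients, and that a larger m reduces borderline flips without abolishing them.

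**Conclusion.** The point holds as a cheap improvement. Five imputations are unjustified in the plan and feed a threshold rule that magnifies small instabilities.

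Over an assumed FMI of 0.05 to 0.23, the efficiency cost is about 0.6% to 4% in interval width. The 8% figure applies only if FMI reached 0.37, which is a ceiling and not an estimate. Validity is not in question.

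The more important effect is that a coefficient with an underlying p of .025 would be lost in about 1% to 25% of imputation runs over that range, against 0.2% or less with 40 imputations. At the low end the problem is slight; at the high end it could change the Tool.

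These figures rest on the assumed FMI range, Rubin's rules with large complete-data degrees of freedom, and imputation draws that behave as approximately normal.

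**What to change.** In the quantitative part of Avoidance of bias, replace 5 with about 40 imputations, and state and report the seed. In the Tool description under Aim 4, specify that backward selection uses Wald tests pooled across the imputed datasets.

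It would also help to name the imputed variables and report the estimated FMI for the main coefficients, so that readers can judge whether 40 was enough.

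The change reduces seed dependence but does not remove it for results very close to .05, and such results should be described as borderline.

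The cost is computer time and a small amount of programming for the pooled selection. No new data or design change is needed.

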#### Sample size

We did power calculation for Aims 2 and 3. Here, we focus on the association between ADL stage and the first comparator, care coordination and quality, in Aim 2, and that between the first comparator and transition in Aim 3.

First, we show the detectable RRRs for associations between ADL stages and the first comparator. Using our preliminary data in Table 2 which included three panels, we assume the distribution of the ADL stages will be similar across 10 years for which we will request the data for the project. After trichotomizing the first comparator, we obtained the proportion for the three categories (1, 2, and 3 from dissatisfied to satisfied) for stage I. They are 13.32%, 60.19%, and 26.49%.

Relative risk of being dissatisfied is defined as the probability of being dissatisfied divided by the probability of being neither dissatisfied nor satisfied. The detectable RRRs comparing other stages to stage I are shown in Table 3. With 10 years of data, we will be able to detect RRRs of 0.91 and 1.07 when comparing stages 0 to I. The RRRs we observed using 1 year data are actually much bigger than these, which indicate that we have adequate power.

Table 3. Detectable RRRs comparing other Stages to Stage I (assuming 80% power and 5% significance level)

	Category 1 versus Category 2	Category 3 versus Category 2
Stage 0 versus I	0.91	1.07
Stage II versus I	1.15	0.89
Stage III versus I	1.16	0.88
Stage IV versus I	1.29	0.80

We then calculate the detectable RRRs when we compare the transition outcome across the three groups for the first comparator. We again assume the distribution of the first comparator will be similar across 10 years and the transition probability for the reference category, "neither dissatisfied nor satisfied," was estimated from the 1 year transition in ADL stages for the three panels that were active in both 2005 and 2006. Relative risk of functional improvement is defined as the probability of ADL functional improvement divided by the probability of being stable in ADL stage. All the detectable risk ratios (Table 4) are smaller than 2 except for one RRR for institutionalization, which indicate ample power for our analysis.

Table 4. Detectable RRRs of transition (functional stable is the reference) for the three categories of the first comparator (assuming 80% power and 5% significance level)

	Death	Institutionalization	Functional deterioration	Functional improvement
Dissatisfied vs. neither dissatisfied nor satisfied	1.71	2.71	1.50	1.49
Satisfied vs. neither dissatisfied nor satisfied	1.24	1.63	1.16	0.90

Qualitative: The SL group analyses will include geographically diverse stakeholders with a variety of socioeconomic circumstances, disabilities, comorbidities, and life circumstances. The SL groups will be computer literate. The addition of Urban groups further enriches the sample

PRINCIPAL INVESTIGATOR (LAST, FIRST, MIDDLE): [name]

by obtaining PWD from a predominantly minority low literacy population. The SL and Urban recruitment strategies enable the inclusion of hard-to-reach people, including those who face numerous disability-related, economic, educational, social class, ethnicity, and cultural barriers.

By design, the MCBS samples are weighted to be representative of the entire elderly and working age Medicare population, and thus by its nature will include a diverse study population. The sample will also have a wide range of medical comorbidities. Preliminary results (Table 5) show diversity with respect to ADL and IADL stage as well as transition outcome status (above). Finally, the sampling frame is designed to be geographically diverse. Table 5 provides sample size estimates from 3 active panels of respondents at the fall 2006 Access to Care interview (about 3/10ths the study sample size). Over 4 and 5 million people had mild ADL or IADL limitations, respectively, with another 4.6 and 7.0 million people having more serious ADL and IADL limitations. Between-group differences across the 5 comparators will be addressed quantitatively according to the transition outcomes with independent effects of ADL and IADL stage determined.

Table 5. Sample size shown for 3 panels; expected size for 10 panels will be 40,000

Stage	Difficulties in ADL			Difficulties in IADL		
	Raw N	Expected N in population (million)	Weighted percent (SE on weighted %)	Raw N	Expected n in population (million)	Weighted percent (SE on weighted %)
0	8208	21.1	69.25 (0.86)	6924	18.2	59.65 (0.97)
I	1942	4.8	15.73 (0.50)	2094	5.3	17.5 (0.59)
II	995	2.4	7.72 (0.37)	1141	2.9	9.45 (0.37)
II	728	1.8	5.97 (0.36)	1558	3.4	11.1 (0.41)
IV	185	0.4	1.33 (0.14)	341	0.7	2.3 (0.15)
Total	12058	30.5	100	12058	30.5	100

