#### **Choice of data for quantitative analyses and Description of Data Sources**

The MCBS is conducted by the Centers for Medicare and Medicaid Services (CMS) through in-person beneficiary or proxy interviews. Respondents are sampled from the Medicare enrollment file to be representative of the Medicare population as a whole. Sample persons are interviewed three times a year for a maximum of four years forming a continuous profile of each individual's personal health care experience. Aims 2, 3, and 4 will apply a decade of data from the MCBS. The MCBS sample was selected for the qualitative aspects of Aims 2, 3, and 4 because these data provide the means to quantify the prevalence of disparities within the Medicare population and any associated outcome burden at the societal level. Also, derivation of the **Patient-Informed Surveillance Tool** within MCBS data will facilitate its potential implementation within Medicare as a means to monitor disparities and outcomes. The oldest old (80 and over) and the young disabled (between the ages of 21 and 64) are oversampled to permit more detailed analyses of these sub-populations. The MCBS applies a rotating panel survey design. A rotating panel will be followed for 12 interviews. There are four panels active at any one time. Each has approximately 4,000 sample persons. New panels introduced each year in the fall round will replace the oldest panel retired the following summer. This project will use the Access to Care files from the MCBS which include all variables needed in the analyses.

**The Study Sample:** An Access to Care file is released within 2 years of the survey. We plan to request 10 panels entering at the time of their fall interview in 2000-2009. Access to Care files in the following 3 fall interviews (2010-2012) will serve to track 1, 2, and 3 year transition outcomes. The sample will include all fee for service and Health Maintenance Organization (HMO) Medicare beneficiaries 21 years of age and older. Those living in institutions at the time of their initial interviews will not be included since institutionalization is an outcome state.

**1. Variable Definition and Measurement (Quantitative).** All variables are available in the MCBS Access to Care files.

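### Table 3's detectable RRRs do not follow from the planned 40,000 respondents: power at the printed values is about 56–63%, not 80%, before any design effect

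*Combined protocol and SAP*

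**What the plan says.** The Aim 2 calculation is in Part C, Sample size. It compares each ADL stage with stage I on the first comparator, split into three categories, with the middle category as base. The stage I percentages for dissatisfied, middle and satisfied are given: "They are 13.32%, 60.19%, and 26.49". Table 3 lists the detectable RRRs at 80% power and a 5% level, and the text reads: "With 10 years of data, we will be able to detect RRRs of 0.91 and 1.07 when comparing stages 0 to I". It concludes: "The RRRs we observed using 1 year data are actually much bigger than these, which indicate that we have adequate power".

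Table 3 comes with no N, formula or design effect. The N has to be taken from three other statements:

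- Choice of data, on the panels: "We plan to request 10 panels entering at the time of their fall interview in 2000-2009", and on their size: "Each has approximately 4,000 sample persons".
- The text before Table 5, which describes its three panels (12,058 people) as "about 3/10ths the study sample size".
- The Table 5 caption: "Sample size shown for 3 panels; expected size for 10 panels will be 40,000".

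Comparators and stages are both taken at the baseline interview, so each person contributes one record. The Data Analysis section sets two-sided tests at .05 and describes a clustered sample with unequal selection probabilities.

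**The concern.** An RRR of 1.07 is a very small effect to detect against a reference stage that makes up about 16% of 40,000 people and then splits into three categories. The plan prints nearly every input to this calculation, so the table should be reproducible. If it is not, the 80% power stated for Aim 2 is not what the design delivers. Aim 2 measures disparities by stage of disability. The group with least information is stage IV, the smallest and most disabled.

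**Working it through.** **Inputs.** N = 40,000. The Table 5 raw ADL counts for stages 0, I, II, III and IV are 8,208, 1,942, 995, 728 and 185 of 12,058. Scaled by 40,000/12,058, these become 27,228, 6,442, 3,301, 2,415 and 614. The stage I probabilities are p1 = 0.1332, p2 = 0.6019 and p3 = 0.2649. The RRR is the ratio, across stages, of P(category 1 or 3)/P(category 2). The test is two-sided at 5%, and sampling is treated as simple random.

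**Formula.** For category k and stage s, with q the stage s probabilities under the alternative:

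Var(log RRR) = 1/(n_I p_k) + 1/(n_I p_2) + 1/(n_s q_k) + 1/(n_s q_2)

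Power = Φ(|log RRR|/SE − 1.960). The detectable RRR solves |log RRR| = (1.960 + 0.842) × SE.

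**One entry in full: stage 0 against I, category 3, printed 1.07.**

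- The divisor is 0.1332 + 0.6019 + 0.2649 × 1.07 = 1.01854, so q3 = 0.2783 and q2 = 0.5909.
- Variance = 0.000586 + 0.000258 + 0.000132 + 0.000062 = 0.001038, so SE = 0.0322.
- log 1.07 = 0.0677 and 0.0677/0.0322 = 2.100. Power = Φ(0.140) = 55.6%.
- At a fixed RRR the variance scales as 1/N, so 80% power needs 40,000 × (2.802/2.100)², about 71,200.

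**All eight entries.** The last column is the smallest N that fits if the printed value may be off by 0.005 through rounding.

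| Stage vs I, category vs 2 | Printed | Detectable at 40,000 | Power at printed value | N for 80% | Lowest N with rounding |
|---|---|---|---|---|---|
| 0, cat. 1 | 0.91 | 0.888 | 60.8% | 62,932 | 56,221 |
| 0, cat. 3 | 1.07 | 1.094 | 55.6% | 71,190 | 62,286 |
| II, cat. 1 | 1.15 | 1.191 | 60.4% | 63,552 | 59,676 |
| II, cat. 3 | 0.89 | 0.867 | 63.1% | 59,650 | 54,374 |
| III, cat. 1 | 1.16 | 1.213 | 56.7% | 69,307 | 65,330 |
| III, cat. 3 | 0.88 | 0.852 | 61.4% | 62,052 | 56,985 |
| IV, cat. 1 | 1.29 | 1.386 | 57.4% | 68,194 | 66,028 |
| IV, cat. 3 | 0.80 | 0.745 | 57.9% | 67,398 | 63,955 |

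No entry is reproduced, and all err in the favourable direction. A two-proportion calculation (55.6–63.3%) and a multinomial simulation with 200,000 replicates (55.6–63.2%) give the same power range. Weighted Table 5 shares give 52–61%.

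**Which N would fit?** Under this two-sided test, a single N of 66,500 gives 0.912/1.073, 1.147/0.896, 1.163/0.884 and 1.294/0.799. Seven of the eight match after rounding, and the eighth (0.896 against 0.89) is within 0.01. Pooling ten yearly cross-sections (10 × 12,058 = 120,580) does not fit: stage 0 would be 0.934/1.053, and power at the printed values about 95–98%.

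**Design effect.** For Table 3 to hold at 40,000, the design effect on the log RRR would have to be 40,000/71,190 = 0.56 to 40,000/59,650 = 0.67, depending on the entry. Clustering and unequal weights normally push it above 1. The Table 5 standard errors imply 1.8–4.2 for stage prevalence; for stage 0, SRS SE = √(0.6925 × 0.3075/12,058) = 0.42%, and (0.86/0.42)² is about 4.2. Those values do not carry over to an RRR, so I take only the direction: power is probably lower still.

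**The case against.** **The hidden N is not identified.** This stands. The 66,500 is back-fitted under one method. A one-sided 5% test with N = 52,500 gives practically the same entries and also matches seven of eight. The rounding floor of about 54,400 likewise holds only for the two-sided test. But 52,500 is not in the plan either, and a one-sided test at 40,000 still reproduces no entry (0.900/1.083 for stage 0, 1.339/0.772 for stage IV; power 68–74%).

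**Other methods come close at 40,000.** Two do:

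- A two-sided test of a ratio of proportions within the two categories gives 0.907/1.064, 1.151/0.903, 1.167/0.891 and 1.289/0.802, with four of eight matching. That is not the RRR the plan defines.
- A one-sided test that counts the whole stage in a two-category contrast matches about five of eight. It departs from the two-sided rule and counts people outside the contrast.

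If either was used, the fault is the method rather than the N, and the table still needs correcting.

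**The practical effect is limited.** This also stands. The 56–63% is power at the printed RRRs, not at the effects the investigators expect. The data are existing survey files, the panels are already chosen, and results will be reported with survey-based confidence intervals. Recalculation changes no design decision. It does change a stated power figure and the support for the adequacy claim.

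**Conclusion.** The concern holds. With 40,000 people counted once, the Table 5 stage shares, the RRR as defined and a two-sided 5% test, Table 3 is not an 80%-power table. Power at its values is 55.6–63.1%, and 80% power would need 49–78% more people than planned. In RRR terms the shift is 0.02 for stage 0, 0.02–0.05 for stages II and III, and 0.05–0.10 for stage IV. This assumes simple random sampling and full use of all 40,000, both of which favour the plan. It does not depend on 66,500 being the N actually used. It does not show that Aim 2 is underpowered for the effects expected, because the observed RRRs are not printed. I make no claim about Table 4 or Aim 3, whose inputs are not given.

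**What to change.** Recompute Table 3 and state its basis beneath it: N = 40,000 with one baseline record per person, the five stage counts, the RRR as defined, the variance formula, a two-sided 5% test, and a design effect for the log RRR estimated from the three preliminary panels. If a different N or method was intended, state it, justify it and reconcile it with Table 5 and the two-sided rule. Print the observed RRRs beside the restated values and rest the adequacy statement on that comparison, stage IV included.

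Two smaller corrections belong in the same edit. The input is cited as "Using our preliminary data in Table 2 which included three panels", but Table 2 lists the comparators and the stage counts are in Table 5. For Table 4, give the N with follow-up, the comparator distribution and the reference transition probabilities.

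The cost is a recalculation and a few lines of text, with no new data. The downside is a less favourable table, most of all for stage IV.

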#### **Outcomes:**

**Aim 2:** Comparators (see description below and in Table 2)

**Aims 3 and 4:** "no change" (individual remains at the same ADL/IADL stage), "functional improvement" (recovery to stage of less functional limitation), "functional deterioration" (reflected in higher ADL/IADL staging), "institutionalization" (long-term institutionalization), or "death."

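### Table 4's functional-improvement column, as described, takes no account of baseline stage, while the Aim 3 models adjust for it; the stated 80% power is then not for the planned contrast

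*Combined protocol and SAP*

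**What the plan says.** - **Sample size, Table 4.** Detectable RRRs for the first comparator (care coordination and quality) are given "assuming 80% power and 5% significance level". In the functional-improvement column they are 1.49 for "Dissatisfied vs. neither dissatisfied nor satisfied" and 0.90 for "Satisfied vs. neither dissatisfied nor satisfied". The text adds: "Relative risk of functional improvement is defined as the probability of ADL functional improvement divided by the probability of being stable in ADL stage". The reference category's transition probabilities come from the 2005-2006 pilot panels but are not printed. Nor are the formula, the N or the comparator distribution used. Stage is not mentioned as a restriction or a stratum. The section concludes that power is ample because all ratios but one, for institutionalization, are below 2.
- **Outcomes, Aims 3 and 4.** Improvement is "recovery to stage of less functional limitation". Table 1 defines stage 0 as no difficulty with any ADL.
- **Data Analysis, general approach.** "All will control for baseline age, gender, race"; the list continues with ADL or IADL stage and proxy status. On testing: "A 2-sided $p<.05$ will be used for all final tests of significance". Aim 3 is a multinomial logistic model with no change as reference.
- **Table 5.** "Sample size shown for 3 panels; expected size for 10 panels will be 40,000". At ADL stage 0 there are 8,208 of 12,058. The Study Sample paragraph excludes people institutionalized at baseline, but not people at stage 0.

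**The concern.** Nobody can move to a better stage from stage 0. Once baseline stage is in the model, the fitted probability of improvement at stage 0 is zero, and those respondents carry no information on whether the comparator is related to improvement rather than stability. In a calculation that ignores stage, the same people make up most of the stable denominator and make the contrast look better informed than it is.

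The improvement result matters here. The pilot data linked poorer perceived quality to improvement. Stakeholders found that illogical and asked whether it would survive adjustment, and the plan says the association may be left out of the final Tool. If power for the adjusted contrast is overstated, a null adjusted result could be read as firmer than it is.

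**Working it through.** **1. Can Table 4 be reproduced?** No. An unadjusted two-proportion calculation with N = 40,000 recovers Table 3 to within about 0.015 (0.906, 1.064, 1.152 and 1.304 against the printed 0.91, 1.07, 1.15 and 1.29), so the same method is plausible for Table 4. Applied to Table 4 with the only comparator split printed (stage I: 13.32 / 60.19 / 26.49%), the 1.49 cell implies that improvers are about 0.9% of improved plus stable. The 0.90 cell implies 9.3-11.4%. The ratio ln(1.49)/|ln(0.90)| = 0.399/0.105 = 3.8, whereas that split would give about √[(1/0.1332 + 1/0.6019)/(1/0.2649 + 1/0.6019)] = 1.3. The inputs actually used cannot be recovered.

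**2. Inputs for the check.** From Table 5, the share at stages I-IV is f = (12,058 - 8,208)/12,058 = 3,850/12,058 = 0.319, or about 12,800 of 40,000. The remaining inputs are assumptions:
- q, the share of stages I-IV that improves: 12-35%
- s, the share of stages I-IV that stays stable: 35-65%, with q + s at most 92%
- s0, the share of stage 0 that stays stable: 80-93%
- the comparator is unrelated to stage, stage is entered as categories, and the adjusted RRR equals the tabulated one

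**3. Formulas.** The variance of the log RRR is proportional to:
- ignoring stage: V_all = 1/(f·q) + 1/(f·s + (1-f)·s0)
- adjusting for stage: V_adj = 1/(f·q) + 1/(f·s)

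Power at the printed RRR = Φ(2.8016/√(V_adj/V_all) - 1.96), where 2.8016 = 1.96 + 0.8416.

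**4. Central case** (q = 0.20, s = 0.50, s0 = 0.88). V_all = 1/0.0639 + 1/0.7587 = 15.66 + 1.32 = 16.98. V_adj = 15.66 + 1/0.1596 = 15.66 + 6.26 = 21.92. The ratio is 1.29 and power is Φ(2.465 - 1.96) = 69%. The detectable RRRs become exp(0.3988·√1.29) = 1.57 and exp(-0.1054·√1.29) = 0.89.

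**5. Range.**

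| q / s / s0 | Variance ratio | Power | Detectable RRRs |
|---|---|---|---|
| 0.05 / 0.65 / 0.90 (below the grid) | 1.06 | 78% | 1.51; 0.90 |
| 0.12 / 0.65 / 0.80 (best grid case) | 1.13 | 75% | 1.53; 0.89 |
| 0.20 / 0.50 / 0.88 | 1.29 | 69% | 1.57; 0.89 |
| 0.35 / 0.35 / 0.93 (worst grid case) | 1.74 | 57% | 1.69; 0.87 |

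**6. If the comparator is related to stage.** In Table 3, dissatisfaction is less common at stage 0 and more common at stages II-IV than at stage I. Those figures are detectable sizes, not estimates, but the text says the observed RRRs are much bigger. Adjusted information is the sum over stages I-IV of m·p(1-p)·ab/(a+b). Here m is the stage's share of the sample times (q + s), p = q/(q + s), and a and b are the stage's proportions in the two comparator categories. The calculation that ignores stage uses the same expression with whole-sample category shares and the middle group's overall probabilities. For the central case:

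| Stage-comparator RRRs against stage I (stages 0, II, III, IV) | Power, 1.49 cell | Power, 0.90 cell |
|---|---|---|
| None | 69% | 69% |
| Table 3's own values | 73% | 67% |
| Stronger, assumed: dissatisfied 0.70, 1.3, 1.4, 1.5; satisfied 1.3, 0.8, 0.75, 0.7 | 80% | 61% |

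**The case against.** The strongest reply is that the plan never says stage 0 was counted. With no formula or probabilities printed, Table 4 cannot be shown to be miscalculated. The 0.90 cell would also fit a calculation already limited to stages I-IV (n about 12,770, about 24% improving). That stands, so the point is conditional. But the table names one stable reference for all four columns, and stage 0 people belong in the other three because they can deteriorate, be institutionalized or die. Nothing signals a different denominator for improvement. If one was used, the plan should say so.

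A reader might take 57-75% as the actual power. The documents do not support that: it follows from assumed rates, and 5% improving gives about 78%. A reader might also infer that any link between comparator and stage makes matters worse. It does not: dissatisfied respondents concentrated at stages where improvement is possible add information to the 1.49 cell, and the loss there can vanish. Only the 0.90 cell moves the other way.

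It can also be said that little turns on this. N is fixed by an existing survey, and the plan's own criterion, ratios below 2, is still met throughout the range in step 5. That stands too, and it limits the point to correcting stated figures.

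**Conclusion.** The mismatch between the calculation as described and the planned model holds. On its natural reading, the improvement column is an unadjusted contrast, while Aim 3 will estimate one to which 68% of the ADL sample contributes nothing. If stage 0 was counted and the comparator is unrelated to stage, power at the printed RRRs is below 80% for any non-zero rates: about 57-75% over the assumed grid and about 78% at 5% improving. With dissatisfaction more common at higher stages, the central case gives 73-80% for the 1.49 cell and 61-67% for the 0.90 cell.

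A reader might go further and conclude that Aim 3 is underpowered or not feasible. The documents do not support that. The detectable RRRs move to about 1.53-1.69 and 0.87-0.89 over the grid with the comparator unrelated to stage, and they probably stay below 2 in any realistic case.

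**What to change.** Recompute the functional-improvement column of Table 4 among respondents at baseline stages I-IV (about 12,800 of 40,000 for ADL), stratified by stage to match the adjusted model. Use the pilot panels' stage-specific improvement, no-change and comparator distributions, so that any link between comparator and stage is taken from data rather than assumed. Print the N, the probabilities, the comparator distribution and the formula beside the new detectable RRRs. Limit the sentence on ample power to what those figures show. If the present column was already restricted to stages I-IV, say so, and show how 1.49 and 0.90 arise from one set of inputs.

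The cost is one recalculation from data the team already holds and one revised table column. No change to the sample, the data request or the models is needed.
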